9.5 POPULATIONS OF ANALYSIS

In accordance with guidance from the International Conference of Harmonization of Technical Requirements for Registration of Pharmaceuticals for Human Use (ICH) guideline ICH E9 Statistical Principles for Clinical Trials (1998), the following population of analysis will be used for all statistical analysis:

- The full analysis set (FAS) includes all randomized subjects who receive any study medication and have at least one post-Baseline assessment.
- The per protocol set (PPS) includes all subjects in the FAS, except for those who are excluded because of major protocol violations, where a major protocol violation is one that may affect the interpretation of study results (e.g., taking less than 50% of prescribed study medication during participation).

Final determinations of the PPS will be made at the masked data review meeting held in accordance with ICH E9 prior to the lock data. The complete specification (made blinded to treatment arm) will be documented in the minutes to the blind data review meeting held prior to lock the data.

- The safety set (SAF) includes all subjects who receive any study medication.

For the purpose of understanding the influence of dropouts on study conclusions, the FAS will be partitioned into subjects who complete (completers) and subjects who do not complete (dropouts).

The FAS will be used for all hypothesis tests of efficacy. Analysis of superiority using the PPS will also be done for supportive analyses. If the PPS does not differ from the FAS by at least 15%, the PPS is considered optional.

The SAF will be used for safety analyses.

9.6 DISPOSITION, DEMOGRAPHIC, AND BASELINE DATA

A tabulation of subject disposition will be presented, including the number screened, the number randomized in each population group, the number dosed in each population group, the number who withdrew prior to completing the study, and reasons for withdrawal.

Demographic and baseline characteristics will be summarized for all randomized patients and for the FAS. Variables of interest include the following:

- Age
- Sex,
- Race,
- Ethnicity
- Medical history
- Prior AD medication
- Height/weight/BMI
- Education level
- ApoE4-carrier status
- Years since diagnosis of AD
- Years since diagnosis of diabetes or HbA1c evaluation of 6.5% or more

Additionally, baseline characteristics will be compared for efficacy measures of MMSE, ADAS-cog14, CDR-sb, FAQ, Amsterdam IADL, ApoE4-carrier status, HbA1c. No formal statistical comparisons will be performed.

9.7 EFFICACY ANALYSIS

Efficacy evaluation will include the primary (ADAS-cog14 for Part 1) and co-primary endpoints (ADAS-cog14 and CDR-sb) for Part 2, key secondary measures, and other efficacy markers.

Statistical analysis will be done on each stage of the study, independently, for the primary / co- primary variables: change from baseline in ADAS-cog14 and change from baseline in CDR-sb. For all other secondary variables, and subgroup analyses, the study as a whole will be used for inferential purposes.

9.7.1 Efficacy Variables of Analysis

9.7.1.1 Primary Efficacy Variables of Analysis

The primary analysis will include assessment of the following variables of analysis.

Learning stage (Part 1)

- Mean change from Baseline to Month 6 in ADAS-cog14

Confirm stage (Part 2)

- Mean change from Baseline to Month 18 in ADAS-cog14
- Mean change from Baseline to Month 18 in CDR-sb

Supportive variables will include mean change from Baseline to Visit in ADAS-cog14 and mean change from Baseline to Visit in CDR-sb.

9.7.1.2 Secondary Variables of Analysis

Part 1 secondary variables of analysis will include.

- Mean change from baseline in CDR-sb at Month 6.
- Mean change from baseline in the FAQ at Month 6.
- Mean change from baseline in the Amsterdam-IADL at Month 6.
- Mean change from baseline in eGFR at Month 6.

Part 2 will include the following secondary variables of analysis:

- Time to decline (to support responder analysis) where the specification of decline will be included in the SAP.

- Mean change from baseline in FAQ score at Month 18
- Mean change from baseline in Amsterdam-IADL score at Month 18
- Mean change from baseline in MMSE score at Month 18
- Mean change from baseline in eGFR at Month 18.
- Mean change from baseline in whole brain volume at Month 18.

9.7.1.3 Other Efficacy Variables of Analysis

Additional efficacy variables of analysis are as follows:

- Mean change from Baseline in hippocampal volume at Month 18.
- Mean change from Baseline in ventricular volume at Month 18.
- Mean change from Baseline in NPI
- Mean change from Baseline in DEMQOL.

9.7.2 Statistical Methodology for Primary Analysis

The primary analysis will use the ITT methodology and a main-effects mixed-models for repeated measures (MMRM) methodology. The MMRM will utilize an unstructured covariance where the number of parameters is “ $t(t+1)/2$ ” where “ t ” is the dimension of the covariance matrix, using PROC MIXED in SAS. In the unlikely event of lack of convergence, Toeplitz structure will be employed where the number of parameters is “ t ” where “ t ” is the dimension of the covariance matrix. Time is considered as a class variable. Analysis will include treatment, time and treatment-by-time interaction as fixed effects, Baseline as covariate, and subject as a random effect. Supportive modeling will also include MMRM main-effects model with treatment, time, and subject.

Model assumptions will be evaluated. If the parametric assumptions are evaluated as inappropriate or violated, rank analogues will be advanced.

The primary analysis will be done for each stage separately. Part 1 will use alpha = 0.0499, which includes an adjustment of 0.0001 for interim analyses performed by the Independent Data Monitoring Committee (IDMC). The alpha adjustment for the IDMC for Part 1 is considered to be negligible, hence, the stated alpha for Part 1 is 0.05 for the 100-patient, 6-month trial. Part 2 will use alpha = 0.049, which includes an adjustment of 0.001 for interim analyses performed by the Independent Data Monitoring Committee (IDMC), thereby preserving the overall study-wise alpha = 0.05. The alpha adjustment of 0.001 is considered to be appropriate for the 200-patient, 18-month study.

Multiple imputations (MI) will be used as a supportive analysis with 100 invocations (acknowledging that more invocations are needed with more missing data). Monte Carlo methods are planned.

An essential component of the thorough analysis includes an assessment of the impact of missing data on study conclusions. As a part of assessing this impact, supportive analysis will include:

- an endpoint analysis (reduction to last-observation-carried-forward, justified in this study based on the monotonic progression of the natural course of AD and assuming no more dropouts in the group treated with azeliragon than in the group treated with placebo)
- a completers analysis (observed cases at endpoint)
- observed cases by assessment time.

Interaction terms will be examined in supportive analyses. In the event of a significant interaction term, the impact on analysis conclusion will be examined. The primary model will not include interaction terms. A key supportive analysis will use the ITT methodology and a main-effects model for ANCOVA adjusting for baseline ADAS-cog14 (CDR-sb) using last-observation-carried-forward (LOCF) methods for missing data, justified based on known profiles of ADAS-cog14 (CDR-sb) in AD patients, which is conservative under the assumption that there are not more dropouts in the active-treated group than the placebo group. Rank ANCOVA will be done as a supportive analysis.

To ensure robustness of analysis conclusions against missingness, multiple imputation methods will also be done to cope with missing data as a key supportive analysis using the final on-treatment assessment of treatment failures as non-missing data at endpoint.

In accordance with the recommendations of the report from the National Academy of Science (NAS) panel *“The Prevention and Treatment of Missing Data in Clinical Trials,”* (National Research Council, 2010), missingness is classified as “missing at random” (MAR) or “missing not at random” (MNAR). When subjects are withdrawn due to treatment failure, this event is considered in this sensitivity analysis to be MNAR, and the endpoint value is taken as the hard endpoint (not imputed) in analysis, operationally, the endpoint analysis is the same as LOCF. Data that are missing for other reasons are considered to be MAR, and standard multiple imputation methods are planned.

Descriptive summaries will be produced of the observed values and change from Baseline in co-primary variables by treatment group at each individual time point and at endpoint (final on-treatment assessment for each subject).

For statistical analyses, 95% confidence intervals will be produced for the least-squares means (LSM) in each treatment group, as well as the LSM differences as compared to placebo. For MMRM and ANCOVA, two-sided p-values will be displayed for the comparison against placebo.

Because there are limited numbers of subjects per center, there will be inadequate power to explore impact of the center effect on study conclusion. Descriptive statistics by center will be presented.

The primary analysis controls alpha through the conditional sequence of hypothesis testing. No further adjustment for multiplicity is necessary.

If the PPS differs from the FAS by more than 15%, the analyses will be replicated on the PPS. If the PPS and the FAS do not differ by more than 15%, analysis may not be done on the PPS. Final judgments will be made at the blind data review meeting in accordance with ICH E9.

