9.0 DATA ANALYSIS/STATISTICAL METHODS

The statistical considerations summarized in this section describe the protocol-defined plan for data analysis of this study. A final and complete Statistical Analysis Plan (SAP) will be finalized prior to unblinding the data from the learning stage of the study (Part 1), possibly updated prior to unblinding the confirmatory stage of the study (Part 2). The SAP will supersede the protocol. Any deviations from the planned analyses will be described and justified in the final integrated study report.

This trial describes two studies (learning stage and confirming stage) with a common infrastructure in a single protocol. Statistical analysis of the clinical efficacy variables will be done for each of the study studies separately. Analysis of MRI volumetric data only applies to part 2 of the study. Statistical evaluation of adverse events will be done by each part separately and also integrated for the study as a whole. Statistical analysis of safety measures that are collected by visit will be done for the study as a whole (combined).

Continuous variables will be presented showing number of observations available, mean, median, minimum, maximum, 1st and 3rd quartiles, and standard deviations (or standard errors, depending on the variable) by visit. Categorical variables will be presented showing frequencies and percentages by visit.

All tests will be 2-sided and use an overall study-wise $\alpha = 0.05$ unless otherwise stated. SAS Version 9.4 or later will be used. Medical dictionary for Regulatory Activities (MedDRA) Version 21.0 or later will be used for coding adverse events. Medications will be coded using WHO Drug Dictionary (WHODD) Version March 2018 or later.

This study features a conditional sequential approach to hypothesis testing to control alpha, similar to methods using Bauer closed procedures.

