9.2 SAMPLE SIZE DETERMINATION

Sample size considerations for Part 1:

Assuming a standard deviation of the change from Baseline to Month 6 in ADAS-cog14 of 4, using alpha = 0.05, a total sample size of approximately 82 subjects in balanced allocation (41 subjects per group) provides at least 90% power to detect a difference between treatment groups of 2.9 using a 2-sided, 2-sample t-test. Assuming a dropout rate of 18% or less, randomization of 100 subjects provides adequate statistical power for Part 1 to demonstrate superiority of azeliragon over placebo based on the ADAS-cog14.

Sample size considerations for Part 2:

Assuming a standard deviation of the change from Baseline to Month 18 in ADAS-cog14 of 7.5, using alpha = 0.049 (to include an adjustment for potential alpha inflation due to the independent data monitoring committee reviews), a total sample size of 120 subjects in balanced allocation (60 subjects per group) provides at least 90% power to detect a difference between treatment groups of 4.5 using a 2-sided, 2-sample t-test. Assuming a dropout rate of 25% or less, randomization of 160 subjects provides adequate statistical power for Part 2 to demonstrate superiority of azeliragon over placebo based on the ADAS-cog14.

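### Part 2 fallback covariance assumes equal variance at every visit, against the protocol's planning SDs of 4 (Month 6) and 7.5 (Month 18); if used for the Month 18 contrast, the standard error is too small

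*Protocol*

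**What the plan says.** Section 9.7.2 of the protocol specifies the covariance: "The MMRM will utilize an unstructured covariance where the number of parameters is" t(t+1)/2. It then gives the contingency: "In the unlikely event of lack of convergence, Toeplitz structure will be employed where the number of parameters is" t. The model has treatment, visit as a class variable and their interaction as fixed effects, with "Baseline as covariate, and subject as a random effect". On the error rate it says "Part 2 will use alpha = 0.049", and section 9.0 says "All tests will be 2-sided".

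Section 9.2 sizes Part 1 with "Assuming a standard deviation of the change from Baseline to Month 6 in ADAS-cog14 of 4" and Part 2 with "Assuming a standard deviation of the change from Baseline to Month 18 in ADAS-cog14 of 7.5". Table 2 schedules ADAS-cog14 after baseline at Months 3, 6, 9, 12, 15 and 18, so t = 6. Section 9.7.1.1 makes the Month 18 change primary for Part 2.

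Neither a heterogeneous structure nor an empirical (sandwich) standard error is named for the fallback. The SAP covers Part 1 only and uses a different model there, so section 9.7.2 is the fullest Part 2 text available.

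**The concern.** The parameter count settles which Toeplitz is meant: one common variance plus t-1 covariances. A heterogeneous Toeplitz would need 2t-1. The fallback therefore assumes that ADAS-cog14 change is as variable at Month 3 as at Month 18, which the sample-size section contradicts.

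The error falls in the worst place. Pooling the variance over visits overstates it early and understates it late, and Month 18 is the primary time point. An understated standard error there gives intervals that are too narrow and a test that rejects too often. ADAS-cog14 is also the first test in the Part 2 sequence, so the rest of the sequence depends on it. The protocol sets aside 0.001 of alpha for the monitoring committee's looks; the possible loss here is far larger.

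**Working it through.** **Inputs from the documents.** SD 4 at Month 6 and 7.5 at Month 18, 60 evaluable per arm, difference 4.5, dropout 25% (section 9.2); two-sided alpha 0.049 (sections 9.0 and 9.7.2); six post-baseline visits (Table 2). **Not in the documents:** SDs at Months 3, 9, 12 and 15, and all between-visit correlations. These are assumed below.

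**1. The plan's own figure.** Standard error = 7.5 × √(2/60) = 1.369, and 4.5/1.369 = 3.286. With z = 1.969 for alpha 0.049, power = Φ(3.286 − 1.969) = 0.906 (0.902 by the noncentral t). Randomized number = 120/(1 − 0.25) = 160. The claim "provides at least 90% power to detect a difference between treatment groups of 4.5" is reproduced, so SD 7.5 is what the design relies on at Month 18.

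**2. Parameter counts at t = 6.** Unstructured 6 × 7/2 = 21; homogeneous Toeplitz 6; heterogeneous Toeplitz 2 × 6 − 1 = 11.

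**3. Variance ratio.** (7.5/4)² = 56.25/16 = 3.5.

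**4. Simple pooling.** With the SD linear in time through the two planning values, the six SDs are 3.125, 4, 4.875, 5.75, 6.625 and 7.5. The mean variance is 182.73/6 = 30.46, so the pooled SD is 5.52 and the ratio r = 5.52/7.5 = 0.736. Type I error = 2 × [1 − Φ(1.969 × r)] = 2 × [1 − Φ(1.449)] = 14.7%.

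**5. Likelihood fit of the homogeneous Toeplitz V to the assumed covariance S**, minimising log|V| + tr(V⁻¹S), same SDs, complete data:

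| Correlation | Fitted SD | r | Type I error |
|---|---|---|---|
| AR 0.8 | 5.61 | 0.748 | 14.1% |
| AR 0.9 | 5.68 | 0.757 | 13.6% |
| Compound symmetry 0.6 | 5.55 | 0.739 | 14.6% |

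At 60 per arm, an SD of 5.61 gives a standard error of 5.61 × √(2/60) = 1.024 in place of 1.369.

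Four ways of interpolating the SDs were crossed with correlations from independence to compound symmetry 0.7 and AR 0.9. On complete data r is 0.73-0.78 and type I error 12.3-15.0%. With 25% dropout spread over the visits, r is 0.71-0.75 and type I error 14.0-16.2%.

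**6. Simulation** (2,500 trials per setting, 60 or 100 per arm, complete data). The homogeneous Toeplitz rejects in 13.0-14.4% of null trials. Visit-specific variances reject in 5.0-5.2% of the same trials.

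**7. Range over the unstated SDs**, by simple pooling with Month 3 set to 4:
- Months 9, 12 and 15 all at 4: (5 × 16 + 56.25)/6 = 22.71, r = 0.635, type I error 21%.
- Months 9, 12 and 15 all at 7.5: (2 × 16 + 4 × 56.25)/6 = 42.83, r = 0.873, type I error 8.6%.

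If Month 3 were also 7.5, more variable than Month 6, then (16 + 5 × 56.25)/6 = 49.54, r = 0.938 and the figure is about 6.5%. That is implausible for change from baseline, but still above 4.9%.

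**8. Treatment main-effect test under the same Toeplitz.** r = 1.00 and type I error 4.9%: no inflation.

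**The case against.** The strongest reply is that several conditions must hold together, and the protocol does not settle them.

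- **Which model.** Section 9.7.2 describes a treatment-by-time model but also calls the primary model main-effects and says that it has no interaction terms. Step 8 shows no inflation for a pure main-effect test. This stands. Such a test would not estimate the Month 18 effect, but that is a separate problem.
- **Which analysis is primary.** The synopsis makes ANCOVA with multiple imputation primary and MMRM supportive. On that reading the fallback touches a supportive analysis only. This stands too.
- **How likely the trigger is.** A reader might infer from the random subject effect alongside an unstructured covariance that non-convergence is to be expected. The term is redundant and not identifiable, but that it would trigger the fallback is not shown. A simulated fit of the unstructured model (six visits, 80 per arm, 25% dropout) converged in 500 of 500 trials in each of three correlation settings. That check used an EM algorithm rather than PROC MIXED and left out the random effect, so it bears on the unstructured model alone.
- **Provenance of the SDs.** The values 4 and 7.5 are planning figures for two separately randomized populations, not two visits of one trial. They are nevertheless the protocol's own figures, under common eligibility criteria.
- **Safeguards.** Model assumptions are to be evaluated, and the LOCF, completers and multiple-imputation analyses do not use the pooled Toeplitz variance, so a discrepancy could show. But the remedy named for violated assumptions is rank analogues, which does not restore visit-specific variances.
- **Provisional text.** The SAP supersedes the protocol and may be updated before Part 2 is unblinded, and several Part 2 features are open. That makes the Part 2 SAP a natural place for the repair; it does not make the present fallback sound.

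**Conclusion.** The point holds as a conditional one. If the unstructured fit fails, the homogeneous Toeplitz is used with model-based standard errors, and the Month 18 contrast comes from the treatment-by-time model, then the standard error is too small: about 25%, with type I error about 12-16% at nominal 0.049. With Month 3 at SD 4 and Months 9 to 15 anywhere from 4 to 7.5, the range is 8.6-21%. The direction follows from Month 18 being the most variable visit; the size depends on the interpolation and the correlations.

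A reader might go further and conclude that the Part 2 primary test, as planned, has an error rate of 13-15%. The documents do not support that. The first-choice structure is unstructured and does not have this problem, no probability of non-convergence has been established, and the protocol is inconsistent about which model and which analysis are primary. The figures also concern the ADAS-cog14 test alone, not the joint co-primary claim. No planning SDs are given for CDR-sb, so no size can be attached there.

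A pre-specified fallback should be valid when invoked. This one conflicts with the protocol's own planning values, and no other passage repairs it.

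**What to change.** In protocol section 9.7.2 or the Part 2 SAP:

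1. Replace the fallback with heterogeneous Toeplitz (11 parameters at six visits), then heterogeneous AR(1).
2. Drop the random subject effect wherever the residual covariance is unstructured, because it is redundant.
3. If sandwich standard errors are used with a structured form, state a small-sample correction, since uncorrected ones can be anti-conservative in small samples.
4. Reconcile the synopsis with the two statements in section 9.7.2, so that one primary analysis is named and it is clear whether the Month 18 contrast comes from a treatment-by-time model.

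The first two changes take about two sentences. The statistical cost is 11 − 6 = 5 more covariance parameters than the present fallback, still 10 fewer than the unstructured form.

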9.7.3 Statistical Methodology for Secondary and Other Efficacy Analysis

Secondary and exploratory endpoints that are measurement variables will use similar statistical methodology to the methodology used for primary analysis. Efficacy variables that are proportions will be analyzed using Mantel-Haenszel test. For the analysis of the categories for responders, a Cochran-Mantel-Haenszel test will be used.

Methodologies for variables that are proportions will include construction of confidence intervals for each treatment group and for the difference between groups. For analysis, Fisher's exact test will be used for single-population analysis, and a Mantel-Haenszel test will be used for analyses combining data across strata.

Methodologies for time-to-event variables will include construction of 95% confidence intervals for each group separately and for the difference between groups. For analysis, a Wilcoxon test will be used for single-population analysis, and a van Elteren test will be used for analyses combining data across strata.

Subgroup analyses will be done as identified in the SAP.

Responders based on the ADAS-cog14 total score will be described using Kaplan-Meier curves using the specification of responder (lack of decline) provided in the SAP. Also, a graphical representation will be defined where the y-axis will show the cumulative percentage of patients who achieved the specific measure of improvement in the ADAS-cog14 total score shown on the x-axis with a separate cumulative percentage curve for each treatment group.

If the distribution of any of the above parameters, key secondary, or other secondary endpoints does not appear to be normally distributed, the rank analogues will be advanced.

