9.3 RANDOMIZATION AND BLINDING**9.3.1 RANDOMIZATION**

This protocol includes two independent randomizations for the two stages of the adaptive study.

Subjects will be screened by Investigators or qualified designees to assess eligibility for randomization into the study. An interactive voice response system (IVRS)/interactive web response system (IWRS) will be used for assignment of treatment.

For each stage of the study, subjects will be enrolled and randomized according to a fixed randomization scheme blocked by study investigative site. There is no other stratification in the randomization scheme for either stage of the study.

Randomization will have balanced allocation (1:1) between azeliragon and placebo. Dropouts will not be replaced.

A randomization plan will be developed to guide the programming and security of the randomization scheme for this study.

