1.10 Adaptive Study

This study is an adaptive trial, which includes 2 studies under the same protocol. This SAP is focused on Part 1 of this adaptive study.

This SAP conforms to standards set forth in *Adaptive Designs for Clinical Trials of Drugs and Biologics Guidance for Industry* (CDER, CBER, November 2019). The intention of the adaptive nature of this protocol is to leverage potential advantages related to statistical analysis as depicted in the FDA final guidance.

2 Statistical Hypotheses

Part 1 has a single primary endpoint (ADAS-Cog14).

The testing sequence will be as follows for strict significance, however proof of concept will be attained by significance in any of the outcomes below (Figure 1):

The first set of hypotheses to be tested is as follows:

H₀₁: The mean change in ADAS-cog14 in the active group is equal to that of the placebo group*.

H₁₁: The mean change in ADAS-cog14 in the active group is not equal (is superior) to that of the placebo group*.

Conditional on statistical significance, testing will proceed hierarchically:

H₀₂: The mean change in A-IADL in the active group is equal to that of the placebo group.

H₁₂: The mean change in A-IADL in the active group is not equal (is superior) to that of the placebo group[§].

Conditional on statistical significance, testing will proceed:

H₀₃: The mean change in CDR-sb in the active group is equal to that of the placebo group.

H₁₃: The mean change in CDR-sb in the active group is not equal (is superior) to that of the placebo group[§].

Conditional on statistical significance, testing will proceed:

H₀₄: The mean change in FAQ in the active group is equal to that of the placebo group.

H₁₄: The mean change in FAQ in the active group is not equal (is superior) to that of the placebo group[§].

H₀₅: The mean change in the cognitive composites or GST in the active group is equal to that of the placebo group.

H₁₅: The mean change in the cognitive composites or GST in the active group is not equal (is superior) to that of the placebo group.

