6.7 Statistical Methodology for Secondary Analysis

Secondary and exploratory endpoints that are measurement variables will use similar statistical methodology to the methodology used for primary analysis and will also use similar figures as those described in the associated TOC. Efficacy variables that are proportions will be analyzed using Mantel-Haenszel test. For the analysis of the categories for responders, a Cochran-Mantel-Haenszel test will be used.

Secondary endpoints will be performed using LZCF as described above. Composite and GST scores will only be run as LZCF.

Methodologies for variables that are categorical and summarized with proportions will include construction of confidence intervals for each treatment group and for the difference between groups. For analysis, Fisher’s exact test will be used for single-population analysis, and a Mantel-Haenszel test will be used for analyses combining data across strata.

Methodologies for time-to-event variables will include construction of 95% confidence intervals for each group separately and for the difference between groups. For analysis, a Wilcoxon test will be used for single-population analysis.

A graphical representation will be defined where the y-axis will show the cumulative percentage of subjects who achieved the specific measure of improvement or worsening in the ADAS-cog14 total score shown on the x-axis with a separate cumulative percentage curve for each treatment group.

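### For time-to-event variables combined across strata, Protocol 9.7.3 names a van Elteren test, which takes no account of censoring; this would reach the Part 2 secondary variable time to decline

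*Protocol*

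**What the plan says.** Protocol 9.7.1.2 lists among the Part 2 secondary variables "Time to decline (to support responder analysis) where the specification of decline will be included in the SAP". Protocol 9.7.3 sets the tests for time-to-event variables: "a Wilcoxon test will be used for single-population analysis, and a van Elteren test will be used for analyses combining data across strata". The same section adds that "Responders based on the ADAS-cog14 total score will be described using Kaplan-Meier curves", with a responder understood as a subject who has not declined. These curves are descriptive. Neither document names a log-rank, Gehan or other censored-data test, or says how a subject who drops out or never declines enters a rank test.

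Protocol 9.2 plans Part 2 for an overall dropout of 25% or less and gives no split by arm.

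The SAP limits its scope: "This SAP is focused on Part 1 of this adaptive study". Its section 6.7 keeps only the first half of the protocol's sentence ("For analysis, a Wilcoxon test will be used for single-population analysis") and does not mention van Elteren. Its variable lists in section 5.1 contain no time-to-event variable.

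**The concern.** A time-to-decline variable observed for 18 months is censored for everyone who leaves early without decline and for everyone still free of decline at Month 18. Kaplan-Meier curves respect that. The van Elteren test is a stratified rank-sum test for fully observed values: each subject supplies one number, and nothing marks whether it is a decline or merely the end of follow-up.

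If follow-up times are ranked as they stand, a dropout at Month 6 counts the same as a decline at Month 6. The arm with more dropout then appears to decline sooner even when the decline rates are identical. The p-value would partly measure retention, and could conflict with Kaplan-Meier curves drawn from the same data.

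Direction matters here. Protocol 9.7.2 defends last-observation-carried-forward on the assumption that azeliragon has no more dropouts than placebo. If placebo does lose more subjects, the error in this test favours azeliragon.

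**Working it through.** **The plan's own figure.** The documents give no error rate or sample size for time to decline, so the nearest figure is the Part 2 calculation in Protocol 9.2 (SD 7.5, difference 4.5, alpha 0.049, 90% power).

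- n per group = 2 × (1.969 + 1.282)² × (7.5/4.5)² = 58.7, so 59.
- At 60 per group the t-test power is 0.902.
- 120/0.75 = 160 randomized.

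The stated figures reproduce. Protocol 3.0 plans 200 subjects, so both 80 and 100 per arm are relevant below.

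**How much censoring.** Let p be the proportion declining by Month 18 (assumed) and d the dropout (25%, the planned ceiling). With independent exponential times, the share with an observed decline is

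ln(1−p) / [ln(1−p) + ln(1−d)] × [1 − (1−p)(1−d)].

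- p = 0.3: 0.357/0.644 × 0.475 = 0.26
- p = 0.5: 0.693/0.981 × 0.625 = 0.44
- p = 0.7: 1.204/1.492 × 0.775 = 0.63

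So roughly 37-74% of the times would be censored.

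**Why unequal dropout biases the ranks.** With no drug effect, the share followed to Month 18 without decline is (1−p)(1−d). At p = 0.5 and dropout 35% v 15%, it is 0.5 × 0.65 = 0.325 against 0.5 × 0.85 = 0.425. The arms differ by 10 points at the longest follow-up time although decline is identical. At p = 0.3 the gap is 0.7 × 0.20 = 14 points; at p = 0.7 it is 0.3 × 0.20 = 6 points. Inflation should therefore be worst when decline is least common.

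**Simulation under no drug effect.** Assumptions not in the documents: the decline rate, the dropout split by arm, four strata, and independent exponential dropout. Assessments are every 3 months to Month 18, matching the Part 2 ADAS-cog14 schedule. Nominal two-sided alpha is 0.05. There were 4,000 runs for van Elteren and 1,500 for the censored-data tests. Type I error with 100 per arm:

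| Decline by Month 18 | Dropout | Van Elteren, event flag ignored | Van Elteren, dropouts and non-decliners last | Stratified Gehan | Stratified log-rank |
|---|---|---|---|---|---|
| 30% | 25 v 25% | 4.9% | 5.0% | 5.5% | 5.3% |
| 30% | 30 v 20% | 18.2% | 6.1% | 4.9% | 5.2% |
| 30% | 35 v 15% | 60.7% | 8.3% | 4.3% | 4.7% |
| 50% | 25 v 25% | 4.8% | 5.3% | 5.4% | 5.1% |
| 50% | 30 v 20% | 14.5% | 5.6% | 4.3% | 4.2% |
| 50% | 35 v 15% | 44.3% | 9.8% | 4.7% | 4.1% |
| 70% | 25 v 25% | 5.0% | 5.1% | 5.4% | 6.1% |
| 70% | 30 v 20% | 10.5% | 6.9% | 5.4% | 5.3% |
| 70% | 35 v 15% | 29.7% | 11.9% | 4.6% | 3.9% |

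With 80 per arm and 70% decline, the event-flag-ignored figures are 9.7% and 25.4% at the two unequal splits. A separate simulation at 100 per arm gave 11-22% and 30-63% over the same decline rates. Together these give the quoted ranges of about 10-22% and 25-63%. A small imbalance does little: at 25% v 20% dropout the error is 6-8%.

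**Direction.** At 100 per arm, 50% decline and 25% v 15% dropout, 14.3% of null trials reject, and only 0.2% of trials reject in favour of the arm with more dropout.

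**The case against.** The case against has four parts.

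1. **Van Elteren may never be used.** It applies only when strata are combined, and none are named for this variable. Apart from blocking by site, "There is no other stratification in the randomization scheme for either stage of the study". Protocol 9.7 does say "For all other secondary variables, and subgroup analyses, the study as a whole will be used for inferential purposes", which could make study part a stratum, but Part 1 lists no time-to-decline variable to combine. This stands as a limit on how likely the harm is. It does not make the named test suitable if strata are used.

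2. **Wilcoxon may already mean the censored-data test.** A reader might infer that the single-population test is also wrong. The documents do not show that. The word stands under time-to-event variables, in the section that plans Kaplan-Meier curves, and the Gehan form holds its error rate as well as log-rank does. Pairing it with van Elteren hints at the rank-sum version, but that makes the term ambiguous, not wrong.

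3. **Details are deferred.** The definition of decline is left to the SAP, and "The SAP will supersede the protocol". A Part 2 SAP can settle all of this. That is true, but until it does, the protocol's named test is the default.

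4. **The size is invented.** A reader might take one of the tabulated error rates as a property of this trial. It is not: the plan gives no split by arm and does not say that dropout times count as decline times. At equal dropout there is no inflation, and ranking non-decliners last removes most of it.

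**Conclusion.** The point holds for van Elteren. It is the named test for time-to-event data across strata, it cannot represent censoring, and the one variable it would serve is certain to be censored. The size depends on the assumed decline rate, the assumed dropout gap and how censored subjects are ranked. It runs from no inflation at equal dropout to several times the nominal level at a 20-point gap with the event flag ignored.

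Two wider readings are not supported. First, a reader might infer that the trial's confirmatory error rate is at risk. Time to decline is not in the Protocol 9.4 sequence (ADAS-cog14, CDR-sb, FAQ, then MRI), so that alpha is untouched; what is at risk is a misleading secondary p-value. Second, a reader might infer that SAP 6.7 must be corrected. It covers Part 1, lists no time-to-event variable and does not name van Elteren, so an edit there would change no listed analysis.

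**What to change.** In Protocol 9.7.3, and in the SAP for Part 2:

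- For time-to-event variables combined across strata, replace van Elteren with a stratified log-rank or a stratified Gehan-Wilcoxon test. Either is adequate; choose one in advance.
- For a single population, state that Wilcoxon means the censored-data (Gehan) version, or name log-rank instead.
- Censor subjects without decline at their last assessment, as the planned Kaplan-Meier curves require.
- Name the strata and give the definition of decline that Protocol 9.7.1.2 defers to the SAP.

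The cost is wording only. The tests are in standard software and no added data or subjects are needed. It should be done before Part 2 is unblinded, so that the test is not chosen with the results in view.
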